### **Outcome of Study:**

The expected outcomes include a reduction in reintubation rates at 48 - 72 hours, 7 days, and 28 days post-extubation in the HFNC group compared to the NIV group. Additionally, this study aims to decrease mortality rates in the CICU and shorten the length of hospital stay for pediatric patients following cardiac surgery.

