**Secondary Objectives:**

1. To compare CICU length of stay between patients receiving HFNC and those receiving NIV.
2. To compare sedation usage (duration and total dose) between patients receiving HFNC and those receiving NIV
3. To compare COMFORT scale between patients receiving HFNC and those receiving NIV

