### **Comparison of the Effectiveness of HFNC and NIV**

Studies comparing HFNC and NIV in pediatric post-cardiac surgery patients have yielded mixed results. Some research supports HFNC as a more comfortable and easier-to-implement modality, particularly due to its less invasive nasal cannula interface compared to the masks used in NIV. Furthermore, HFNC is considered more user-friendly in non-ICU settings. Conversely, NIV has been utilized for a longer duration in intensive care settings and is known for providing stable positive pressure, which helps prevent alveolar collapse and improves gas exchange in patients with compromised pulmonary function.

[figure not shown]
A study by Zhou et al. (2024) found that HFNC significantly reduced reintubation risk (RR = 0.36,  $P < 0.00001$ ) and shortened ICU stay duration (MD = -4.75,  $P = 0.04$ ). Similarly, research by Elmitwalli et al. (2024) reported that HFNC decreased reintubation rates (RR = 0.45,  $P < 0.01$ ), mortality (RR = 0.31,  $P < 0.01$ ), as well as length of hospital stay (-8.76 days,  $P < 0.01$ ) and ICU stay (-4.63 days,  $P = 0.04$ ). However, compared to conventional oxygen therapy, no significant differences were observed in reintubation rates. A study by Kuitunen (2023) concluded that there was insufficient evidence to establish a definitive difference in reintubation rates and other clinical outcomes between different non-invasive ventilation strategies, due to high bias risk and limited study numbers.

The debate continues regarding which modality is more effective in reducing extubation failure and mortality. HFNC provides benefits for patients with moderate-to-severe respiratory failure risk, whereas NIV may be more suitable for patients with severe pulmonary conditions. Further research is required to determine the optimal post-extubation strategy for pediatric post-cardiac surgery patients.

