	T-piece	Ventilator weaning method using a T-Piece without pressure support.	Categorical	Medical Records on the Method Used	
ABG 1 hour after NIV/HFNC	pH	Arterial blood pH measured 1 hour after initiation of NIV or HFNC.	Numeric	Arterial Blood Gas (ABG) Measurement	
	PCO2	Partial pressure of carbon dioxide (PaCO2) in blood, measured 1 hour after initiation of NIV or HFNC	Numeric	Arterial Blood Gas (ABG) Measurement	
	PaO2	Partial pressure of oxygen (PaO2) in blood, measured 1 hour after initiation of NIV or HFNC	Numeric	Arterial Blood Gas (ABG) Measurement	
	BE (Base Excess)	Base excess or deficit in blood, measured 1 hour after initiation of NIV or HFNC	Numeric	Arterial Blood Gas (ABG) Measurement	
	HCO3	Bicarbonate concentration in blood, measured 1 hour after initiation of NIV or HFNC	Numeric	Arterial Blood Gas (ABG) Measurement	
	PF ratio	Ratio of PaO2 to FiO2, measured 1 hour after initiation of NIV or HFNC	Numeric	Arterial Blood Gas (ABG) Measurement	
	OI/OSI	Oxygenation Index (OI) or Oxygen Saturation Index (OSI), measured 1 hour after initiation of NIV or HFNC	Numeric	Arterial Blood Gas (ABG) Measurement	
Successful Extubation	No Reintubation in 72 hours	Patient does not require reintubation within 72 hours after extubation	Categorical	Based on Clinical Observation	
Extubation Failure	Reintubation within 72 hours	Patient requires reintubation within 72 hours after extubation	Categorical	Based on Clinical Observation	
Reintubation	Reintubasi at 72 hours, 7 days and 28 Days	Frequency of patients requiring reintubation at 72 hours, 7 days and 28 days	Categorical	Based on Clinical Observation	
Mortality in CICU	Mortality During CICU Stay	Number of patient deaths during CICU hospitalization	Categorical	Based on Mortality Records	
Length of CICU Stay	Total Length of CICU Stay (in Days)	Total length of CICU stay measured in days	Numeric	Based on Hospital Records	
Length of Hospital Stay	Total Length of Hospital Stay (in Days)	Total length of hospital stay measured in days	Numeric	Based on Hospital Records	
Sedation usage	Duration of sedation (in Hours) and total dosage	Total duration of sedation after extubation measured in hours and total dosage	Numeric	Based on Hospital Records	
COMFORT scale	Patient's comfort during sedation post extubation	Patient's comfort measured in COMFORT behavioral scale	Categoric	COMFORT behavioural scale assessment	

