## CHAPTER IV Research Methodology

### 4.1. 4.1. Study Design

This study employs a Randomized Controlled Trial (RCT) design to compare two intervention groups: patients receiving oxygen therapy using Non-Invasive Ventilation (NIV) and those receiving therapy with High Flow Nasal Cannula (HFNC) using AirvoTM3 Nasal High Flow/HFNC System. Patients will be monitored for the incidence of extubation failure and other clinical parameters throughout their hospitalization.

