#### **4.7. Data Collection Technique**

[figure not shown]
Data is collected through clinical observation and measurement of patients' respiratory parameters before and after therapy. A blood sample of 0.5–1.0 mL is taken one hour before and after therapy. Monitoring is conducted by a trained medical team, and data on extubation failure, vital parameters, and patients' clinical conditions are continuously recorded during hospitalization.

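### Death is counted only while the child is in the CICU, a window whose length the trial compares between arms, so the arm that leaves sooner can look safer without a true difference

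*Protocol*

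**What the plan says.** Table 1 of the Protocol (Chapter III) defines mortality in the CICU as "Number of patient deaths during CICU hospitalization". The section on the outcome of the study uses the same window: "this study aims to decrease mortality rates in the CICU and shorten the length of hospital stay". Section 4.3 gives mortality its own sample-size calculation, 0.10 with HFNC against 0.35 with NIV. No section defines death to hospital discharge or to a fixed day.

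The secondary objectives in section 1.5 include "To compare CICU length of stay between patients receiving HFNC and those receiving NIV". Chapter II, on the comparative effectiveness of HFNC and NIV, cites one meta-analysis in which HFNC "shortened ICU stay duration (MD = -4.75", with no unit printed, and another reporting "ICU stay (-4.63 days".

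Reintubation, in the same Table 1, has fixed horizons: "Frequency of patients requiring reintubation at 72 hours, 7 days and 28 days". Section 4.1 says children are monitored for "other clinical parameters throughout their hospitalization", and section 4.7 says data are "continuously recorded during hospitalization".

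**The concern.** A mortality comparison is fair when both arms are observed for the same time. Here each child's observation for death ends at CICU discharge, an event that treatment may bring forward. If one arm is discharged earlier, its children have fewer days in which a death can count. A death on the ward or at home is left out in either arm, but more of the risk period is left out in the arm that leaves sooner.

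Two errors could follow. Equal mortality could appear as a benefit of the arm with the shorter stay. An excess of deaths after early step-down would fall outside the defined outcome. Mortality is a stated aim, and section 1.7 intends the results to feed clinical practice guidelines at the hospital. Table 1 also gives the less serious event, reintubation, a common 28-day horizon and gives death none.

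**Working it through.** **The plan's own mortality figure.** Inputs from section 4.3: P1 = 0.10, P2 = 0.35, z-values 1.96 and 0.84, mean P = 0.225, Q = 0.775.

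n = [1.96 × √(2 × 0.225 × 0.775) + 0.84 × √(0.10 × 0.90 + 0.35 × 0.65)]² / 0.25² = 42.55

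The protocol prints 42.54, rounded to 43, so the figure reproduces. It does not depend on how deaths are counted and does not govern the trial size, because section 4.3 adopts 51 per group before inflation.

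**Illustration of the mechanism.** From the documents:
- 13.6% site mortality after paediatric cardiac surgery (section 1.1, no time horizon given)
- ICU stay 4.63 days shorter with HFNC (Chapter II)
- 57 children per arm (section 4.3)

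Assumed:
- 13.6% is the true mortality by day 28 after extubation in both arms.
- Every NIV child leaves the CICU at day L and every HFNC child at day L − 4.63.
- L is 7, 10 or 14 days.
- Deaths follow one of three time patterns.

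For constant hazard, h = −ln(1 − 0.136)/28 = 0.00522 per day, and counted mortality is 1 − exp(−h × days). For earlier deaths with exponential mean τ, truncated at day 28, it is 0.136 × [1 − exp(−days/τ)] / [1 − exp(−28/τ)]. The last column is the difference in proportions × 57.

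| Timing of deaths | L (days) | NIV | HFNC | Apparent RR | Fewer deaths counted per 57 |
|---|---|---|---|---|---|
| Constant hazard | 7 | 3.59% | 1.23% | 0.34 | 1.3 |
| Constant hazard | 10 | 5.09% | 2.76% | 0.54 | 1.3 |
| Constant hazard | 14 | 7.05% | 4.77% | 0.68 | 1.3 |
| τ = 7 days | 7 | 8.76% | 3.98% | 0.45 | 2.7 |
| τ = 7 days | 10 | 10.53% | 7.42% | 0.70 | 1.8 |
| τ = 7 days | 14 | 11.98% | 10.22% | 0.85 | 1.0 |
| τ = 3 days | 7 | 12.28% | 7.43% | 0.60 | 2.8 |
| τ = 3 days | 10 | 13.12% | 11.33% | 0.86 | 1.0 |
| τ = 3 days | 14 | 13.47% | 13.00% | 0.97 | 0.3 |

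If the other cited figure, 4.75, is read as days (an assumption), constant hazard gives:
- 10 against 5.25 days: 5.09% against 2.70%, RR 0.53
- 15 against 10.25 days: 7.53% against 5.21%, RR 0.69
- 8 against 3.25 days: 4.09% against 1.68%, RR 0.41

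The differences of 2.39, 2.32 and 2.41 percentage points, times 57, are 1.36, 1.32 and 1.37 deaths.

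Counted to day 28 in every child, both arms show 13.6% and the RR is 1.00 in every scenario.

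**The case against.** The strongest reply is that the bias is only possible. It needs both a real difference in CICU stay and deaths after CICU discharge. If every death happens in the CICU, it vanishes. Section 1.1 attributes mortality mainly to low cardiac output, arrhythmia, multi-organ dysfunction and extubation failure. Such deaths may well come early, and the early-death rows with longer stays show little distortion. This stands, and it is why the range has to reach 0.97.

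The inputs are also soft. The 13.6% covers paediatric cardiac surgery patients at the site. Trial children have passed an extubation readiness test but are selected as high risk, so their mortality could lie on either side. A shorter CICU stay is not the protocol's own prediction: section 1.5 only compares it, and the outcome section expects a shorter hospital stay. Chapter II also cites a review that found the evidence insufficient. All of this stands, and it limits the size of the point without removing the mechanism.

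Mortality is neither the primary outcome nor among the listed objectives in section 1.5. That also stands and keeps the point modest.

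A reader might infer from sections 4.1 and 4.7 that data collection stops at hospital discharge, so that day-28 status is never observed in children discharged earlier. The text does not say that. It describes recording during the hospital stay and states no end of follow-up. Table 1 sets a 28-day reintubation outcome, and section 4.3 allows 10% for loss to follow-up. What can be said is that no method for establishing day-28 status after discharge is given.

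**Conclusion.** The point holds as a weakness in the definition of a stated but non-primary outcome. The death window ends at a post-randomisation event that the trial compares between arms, and nothing else in the protocol counts later deaths. The primary comparison of extubation failure is not affected.

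Under the assumptions above, equal true mortality could appear as an RR of 0.34 to 0.97 in favour of the arm that leaves sooner. That is 0.3 to 2.8 fewer deaths counted in an arm of 57, and 1.3 to 1.4 under constant hazard. These figures illustrate the mechanism and do not forecast the trial's result.

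A reader might go further and conclude that HFNC will look safer, or that an excess of later deaths would go unseen. The documents support neither. They do not split deaths by place or time. Monitoring runs through the hospital stay, so ward deaths should be in the record even though the defined outcome leaves them out.

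**What to change.** In Table 1 and in the section on the outcome of the study, define mortality as death from any cause within 28 days of the index extubation, wherever it occurs. This matches the longest reintubation horizon already in Table 1. Keep death in the CICU as a descriptive result.

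In section 4.7, state that vital status and reintubation are ascertained at day 28 for children discharged earlier, by a check of clinic or readmission records or one telephone call.

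The cost is amended wording plus one check or call per child discharged before day 28, with some possible loss to follow-up. In-hospital deaths after transfer from the CICU should need no new collection, since monitoring already covers the hospital stay. Treatment and sample size do not change. The amendment is worth making while children can still be reached at day 28.

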#### 4.4. Inclusion and Exclusion Criteria

**Inclusion Criteria:**

- Patients under 18 years of age.
- Post-cardiac surgery patients in the CICU of RSUPN.
- Patients at high risk of extubation failure (e.g., young age, open sternotomy, mechanical ventilation >48 hours).
- Patients who pass the extubation readiness test and spontaneous breathing trial.

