#### **4.6. Sampling Method**

Sampling is conducted consecutively from pediatric post-cardiac surgery patients who meet the inclusion criteria during the study period in the CICU of RSUPN Cipto Mangunkusumo. Subjects meeting the inclusion and exclusion criteria will be randomized into two intervention groups: the High Flow Nasal Cannula (HFNC) group and the Non-Invasive Ventilation (NIV) group, using a simple randomization method. Block randomization was employed to ensure balanced allocation between the intervention and control groups. Subject assignment within each block was conducted randomly using statistical software (e.g., SPSS or Excel), with allocation concealed from investigators involved in data collection to minimize potential bias.

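### CICU and hospital stay are counted as total days, so they include time before allocated support; this adds noise and lowers power for a secondary outcome without biasing the difference in days

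*Protocol*

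**What the plan says.** Chapter III, Table 1, defines the two stay variables as "Total length of CICU stay measured in days" and "Total length of hospital stay measured in days", both from hospital records. Neither row names a starting event. The sedation row that follows does: "Total duration of sedation after extubation measured in hours and total dosage".

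CICU stay is the first of the secondary objectives in section 1.5: "To compare CICU length of stay between patients receiving HFNC and those receiving NIV". Hospital stay is not on that list. It appears in Table 1 and under Outcome of Study, where the aim is to "shorten the length of hospital stay for pediatric patients following cardiac surgery".

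On timing, section 4.4 admits "Patients who pass the extubation readiness test and spontaneous breathing trial", and section 4.6 states that "Subjects meeting the inclusion and exclusion criteria will be randomized into two intervention groups". The population in section 4.4 is "Patients at high risk of extubation failure (e.g., young age, open sternotomy, mechanical ventilation >48 hours", so ventilation beyond 48 hours is one example of high risk and not a requirement.

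**The concern.** HFNC or NIV starts at extubation. A child ventilated for more than 48 hours has already spent at least two days on the ventilator by then, and total hospital stay also counts any days before surgery. The allocated device cannot shorten any of this time.

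Total stay is therefore the sum of a part that the device may affect and a part fixed before allocation. If the fixed part varies widely between children, it blurs the comparison named in the first secondary objective. A chance difference between arms in ventilation time before extubation would also appear as a difference in stay.

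**Working it through.** **1. What the protocol computes.** Section 4.3 sizes the trial on extubation failure (0.42 v 0.17, z values 1.96 and 0.84). Its formula gives 50.98, hence 51 per group. With 10% added, 102 + 10.2 = 112.2, rounded to 113 and then to 57 per group. This reproduces. There is no SD, effect size or power for stay, so there is no stay figure to reproduce. All stay inputs below are assumptions; only the 57 per group and the two-sided 5% level come from the protocol.

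**2. Bias.** Write total = pre + post, where pre is time before extubation and post is time after it. Pre is fixed before allocation, so its expected difference between arms is zero. The expected difference in total days therefore equals the expected difference in post days.

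Illustration: let post be log-normal with median 4 days and log SD 0.65, shortened by 30% in one arm. The control mean is 4 × exp(0.65²/2) = 4.94 days, so the difference is 0.30 × 4.94 = 1.48 days. Simulation gives about −1.5 days on both definitions.

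**3. Dilution of a relative effect.** If pre has median 4 days and log SD 0.7, its mean is 4 × exp(0.7²/2) = 5.11 days. The same 1.48 days is 30% of 4.94 but only 1.48/(4.94 + 5.11) = 15% of the total.

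**4. Variance (normal approximation).** Let r = SD of pre / SD of post, and let ρ be their correlation. Then

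SD(total) = SD(post) × √(1 + r² + 2ρr).

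Take the effect that has exactly 80% power on post days at 57 per group: (1.96 + 0.84) × √(2/57) = 0.525 SD of post. The number per group that restores 80% on total days is 57 × (1 + r² + 2ρr).

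| r | ρ | 1 + r² + 2ρr | Power on total days | n per group for 80% |
|---|---|---|---|---|
| 0.25 | 0 | 1.0625 | 78% | 61 |
| 0.5 | 0 | 1.25 | 71% | 72 |
| 1 | 0 | 2 | 51% | 114 |
| 2 | 0 | 5 | 24% | 285 |
| 1 | −0.3 | 1.4 | 66% | 80 |
| 1 | 0.5 | 3 | 37% | 171 |
| 0.5 | −0.3 | 0.95 | 82% | 55 |

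**5. Simulation (skewed data, rank test).** 57 per arm, post as in step 2, pre log-normal and unaffected by arm. An unadjusted Wilcoxon test on post days has about 80% power throughout. The last column analyses log(total) adjusted for log(pre).

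| Pre: median, log SD, ρ | Wilcoxon on total | Total, adjusted for pre |
|---|---|---|
| 2.5 d, 0.4, 0 | about 70% | 79% |
| 3 d, 0.6, 0 | about 56% | 79% |
| 4 d, 0.7, 0 | about 39% | 75% |
| 4 d, 0.7, 0.4 | about 31% | 85% |

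Repeat runs move these figures by one or two points. With pre at 3 d and log SD 0.6, Wilcoxon power on total days is about 44% at ρ = 0.4 and about 67% at ρ = −0.3.

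**The case against.** A reader might infer that counting total days hides any device effect or biases the comparison. The documents do not support that. Section 4.6 randomises children who already meet the criteria, so pre-extubation days are balanced in expectation, and the mean difference in days is the same on both definitions. The harm is loss of precision.

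The size of that loss is also uncertain. The protocol gives no stay distributions, section 4.8 names no test for stay, and that choice may sit in a SAP that is not shown. If pre-extubation time varies little, the loss is small (78% at r = 0.25). With negative correlation it can vanish (82% at r = 0.5, ρ = −0.3). Adjusting total stay for pre-extubation days recovers most or all of it. These points stand, and they rule out quoting any single power figure as the cost.

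Total stay is also a legitimate measure of resource use over the whole episode, and the protocol does not call it a measure of recovery after extubation. That is a reason to keep it as a description. It is a weaker reason to make it the between-arm outcome for treatments that begin at extubation.

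The possibility of adjustment does not dispose of the point. Table 1 as shown defines no variable for ventilation time or CICU days before extubation, and the only multivariable method in section 4.8 is logistic regression for extubation failure.

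**Conclusion.** The point holds as one of precision. Table 1 fixes both stay outcomes as totals that include days before allocated support, although the same table counts sedation from extubation. The expected difference in days is unbiased. The extra days add variance, dilute a relative effect and expose the comparison to chance imbalance.

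Under the assumed distributions, an unadjusted rank test at 57 per arm falls from about 80% to between about 30% and 70%. The low end needs long, highly variable ventilation that is positively correlated with later stay, and the documents do not show whether this population is like that.

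One further assumption concerns timing. The protocol does not state the exact moment of randomisation; that it follows the readiness test is inferred from the eligibility criteria.

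The effect is confined to CICU stay, a secondary objective, and hospital stay, an expected outcome. The primary comparison and the sample size are untouched. The change is worth making because it is cheap, not because the trial fails without it.

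**What to change.** In Table 1, define the between-arm outcomes as days from index extubation (or from randomisation) to CICU discharge, and from the same point to hospital discharge. Keep total CICU and total hospital stay as descriptive variables. Index extubation is the natural start, since the 72-hour outcome and the sedation row already use it.

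The alternative is to keep total stay as the outcome, add time from CICU admission (and, for hospital stay, from hospital admission) to extubation as a defined variable, and adjust the comparison for it.

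The first option costs a short edit to two rows of Table 1. Extubation time is already needed for the 72-hour outcome and discharge dates for the stay outcomes, so it needs no new patients or measurements. The only loss is that the whole-episode measure of resource use becomes descriptive.

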### CHAPTER III Theoretical Framework, Conceptual Framework, and Operational Definitions

**Image 1. Theoretical Framework**

**Image 2. Conceptual Framework**

**Table 1. Operational Definitions**

Variable	Definition	Scale	Measurement Criteria
Age	Age <12 months	Patient age categorized as less than 12 months.	Categorical
	Age >12 months	Patient age categorized as more than 12 months.	Categorical
Weight	Weight	Patient weight measured using a scale before intervention.	Numeric
RACHS	RACHS	Risk stratification for cardiac surgery.	Categorical Ordinal
Operation Type	Off CPB	Surgery without the use of cardiopulmonary bypass.	Categorical
	CPB	Surgery without the use of cardiopulmonary bypass.	Categorical
Gender	Male	Male patient.	Categorical
	Female	Female patient.	Categorical
Malnutrition	Yes	Patient diagnosed with malnutrition based on clinical assessment.	Categorical
	No	Patient not diagnosed with malnutrition based on clinical assessment.	Categorical
Respiration Diagnosis at Extubation	Pneumonia	Patient diagnosed with pneumonia at the time of extubation.	Categorical
	Effusion	Patient diagnosed with pleural effusion at the time of extubation.	Categorical

Vasoactive-Inotropic Score before Extubation	VIS	Vasoactive-Inotropic Score (VIS) to assess inotropic and vasoconstrictor therapy before extubation.	Numeric	VIS based on Drug Dosage	Calculation on Drug Dosage
ABG 1 hour before extubation	pH	Arterial blood pH measured 1 hour before extubation.	Numeric	Arterial Blood Gas (ABG) Measurement	
	PCO2	Partial pressure of carbon dioxide (PaCO2) in blood, measured 1 hour before extubation	Numeric	Arterial Blood Gas (ABG) Measurement	
	PaO2	Partial pressure of oxygen (PaO2) in blood, measured 1 hour before extubation	Numeric	Arterial Blood Gas (ABG) Measurement	
	BE (Base Excess)	Base excess or deficit in blood, measured 1 hour before extubation	Numeric	Arterial Blood Gas (ABG) Measurement	
	HCO3	Bicarbonate concentration in blood, measured 1 hour before extubation	Numeric	Arterial Blood Gas (ABG) Measurement	
	PF ratio	Ratio of PaO2 to FiO2, measured 1 hour before extubation	Numeric	Arterial Blood Gas (ABG) Measurement	
	OI/OSI	Oxygenation Index (OI) or Oxygen Saturation Index (OSI), measured 1 hour before extubation	Numeric	Arterial Blood Gas (ABG) Measurement	
Weaning Method	Pressure Support	Ventilator weaning method with pressure support.	Categorical	Medical Records on the Method Used	

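### Sedation use and COMFORT are defined only after extubation, with no pre-extubation value to adjust for: a cheap, low-severity gain in precision for two of the three secondary objectives

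*Protocol*

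**What the plan says.** Section 1.5 lists three secondary objectives. The second is "To compare sedation usage (duration and total dose) between patients receiving HFNC and those receiving NIV" and the third is "To compare COMFORT scale between patients receiving HFNC and those receiving NIV". The first, CICU length of stay, is not affected by this point.

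Table 1 (Chapter III) defines the sedation outcome as "Total duration of sedation after extubation measured in hours and total dosage", numeric and taken from hospital records. It defines the COMFORT outcome as "Patient's comfort during sedation post extubation", scored on the COMFORT behavioural scale and typed as categorical. No row records either quantity before extubation.

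The same table does record other quantities before extubation. One is the "Vasoactive-Inotropic Score (VIS) to assess inotropic and vasoconstrictor therapy before extubation". The others are pH, PCO2, PaO2, base excess, bicarbonate, PF ratio and OI/OSI one hour before extubation, all repeated one hour after the device is started. Section 4.7 describes before-and-after measurement for respiratory parameters only. Section 4.8 names a logistic regression for extubation failure and no baseline adjustment for sedation or COMFORT.

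**The concern.** The sedation count starts at extubation. Any sedative still running or being tapered then was set during invasive ventilation, before the assigned device could act, yet it counts in full towards the outcome. Section 4.4 enrols "Patients at high risk of extubation failure (e.g., young age, open sternotomy, mechanical ventilation >48 hours"), so some carry-over is plausible. That is an assumption, because the protocol gives no sedation figures.

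If children differ widely in what they carry over, that spread becomes noise in the comparison between arms, and a chance imbalance in it cannot be corrected. The expected-outcomes paragraph anticipates an HFNC success rate comparable to NIV together with better comfort. If extubation failure proves similar, sedation and COMFORT become much of the remaining argument for either device. A statistical analysis plan can add a covariate, but it cannot supply a bedside score that was never taken.

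**Working it through.** **The plan's own sample size.** Section 4.3 uses P1 = 0.42, P2 = 0.17, mean P = 0.295, z = 1.96 and 0.84:

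n = [(1.96·√(2·0.295·0.705) + 0.84·√(0.42·0.58 + 0.17·0.83)) / 0.25]² = [(1.264 + 0.521) / 0.25]² = 50.98, so 51 per group.

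Allowing for 10% loss, 102/0.9 = 113.3, so 114 in total and 57 per group, as stated. This size is set by extubation failure. The protocol gives no SD, effect or power for sedation or COMFORT, so what follows is conditional.

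**Precision without a baseline.** With n per arm and outcomes in SD units, the standard error of the difference between arms is √(2/n). At 57 per arm it is √(2/57) = 0.187 SD. The difference detectable with 80% power at two-sided 5% is (1.960 + 0.842) × 0.187 = 0.525 SD.

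**Precision with a baseline.** Adjusting for a baseline that correlates r with the outcome multiplies the variance by 1 − r². The detectable difference becomes 0.525·√(1 − r²), and the equivalent unadjusted size is 57/(1 − r²). Power is shown for two assumed effects: a difference of 0.5 SD, and a 40% reduction in sedation with log-scale SD 1.0 (|ln 0.6| = 0.511 SD). In both cases power is Φ(effect / [0.187·√(1 − r²)] − 1.96).

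| r (assumed) | Variance removed | Fall in SE | Detectable difference (SD) | Equivalent n per arm | Power at 0.5 SD | Power at 40% reduction |
|---|---|---|---|---|---|---|
| 0 | 0% | 0% | 0.525 | 57 | 76.1% | 78% |
| 0.2 | 4% | 2.0% | 0.514 | 59 | 77.8% | 79% |
| 0.3 | 9% | 4.6% | 0.501 | 63 | 79.9% | 82% |
| 0.5 | 25% | 13.4% | 0.454 | 76 | 86.9% | 88% |
| 0.7 | 49% | 28.6% | 0.375 | 112 | 96.2% | 97% |

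If only 51 per arm are analysed, the detectable difference goes from 0.555 to 0.480 SD at r = 0.5.

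**Chance imbalance.** By chance alone, the baseline difference between arms lies within ±1.96 × 0.187 = ±0.367 SD in 95% of trials. Unadjusted, an imbalance at that limit shifts the outcome difference by r × 0.367: 0.07 SD at r = 0.2, 0.18 SD at r = 0.5 and 0.26 SD at r = 0.7.

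**Limits.** The table treats sedation as a continuous, roughly log-normal quantity. Children with zero sedation after extubation are not modelled. Nothing here was calculated for COMFORT.

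**The case against.** The strongest reply is that nothing here is wrong. The outcome is coherently defined as sedation after extubation, carry-over falls on both randomised arms, and how fast remaining sedation is withdrawn may be part of what the trial compares. Covariates for secondary outcomes are commonly left to the statistical analysis plan. This stands, and it is why the point is an improvement and not an error.

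A reader might infer more than the protocol supports in four ways:

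- **That the comparison is biased.** It is not. Allocation is randomised, and only precision and chance imbalance are at issue.
- **That the arms can be compared only on raw amounts.** Age, weight, RACHS, the vasoactive-inotropic score and weaning method are all recorded and could be adjusted for. They may share some variance with prior sedation, so the gain over a model that already uses them could be smaller than the table shows.
- **That one chart value would recover the lost precision.** Two baselines are needed, and each removes only r² of its own outcome's variance. Only sedation is stated to come from hospital records.
- **That the sedation baseline is lost.** It can probably be retrieved from those records later. For COMFORT, nothing shows that it is scored before extubation.

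Eligibility may also narrow the carry-over. Children must pass a readiness test and a spontaneous breathing trial (section 4.4), and decreased consciousness is an exclusion. Less spread at baseline tends to lower r. Ventilation beyond 48 hours is only one of several examples of high risk. Finally, the flowchart and group-procedure images are not shown and could list further measurements.

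The gap in the listed variables remains. A plan written later can choose a model, but it cannot adjust for a COMFORT score that was never taken.

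**Conclusion.** The point holds as a low-severity, cheap improvement. Sedation use and COMFORT have no pre-extubation value in Table 1, while the vasoactive-inotropic score and blood gases do. Two of the three secondary objectives are affected.

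For sedation the size of the gain depends on a correlation that the protocol does not give. At r of 0.3 or below the standard error falls by less than 5%, which is little. From about 0.5 the gain is material, equal to roughly 19 more children per arm (76 against 57). These figures assume a continuous outcome on the log scale and 57 analysed per arm; the power figures also assume the stated effects.

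For COMFORT the size is unquantified. A reader might carry the sedation figures across, but Table 1 types COMFORT as categorical. Its scores before and after extubation are also taken under different conditions, and their correlation is unknown. The primary outcome and its sample size are unaffected.

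**What to change.** Add to Table 1:

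1. Sedative exposure in the 24 hours before extubation, and whether an infusion was running at extubation. Abstract both from the hospital records already used for the sedation outcome, and record dose in the same way as after extubation so the two can be paired.
2. One COMFORT behavioural score just before extubation.

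Then adjust each outcome for its own baseline. For sedation, use ANCOVA on the log scale, or a rank-based or two-part model if zeros are common. For COMFORT, use an ordinal model with the baseline score as covariate if it is kept categorical, or ANCOVA if it is analysed as a score. Fix these models before outcome data are compared by arm.

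The cost is one chart field, one brief bedside score on a scale already in use, and one baseline adjustment per secondary model. No extra patients or staff are needed and treatment does not change. Sedation before extubation can be abstracted retrospectively for children already enrolled. A COMFORT score cannot be recovered unless it happened to be charted, so that item is the time-sensitive one.
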